6.2.2 Temozolomide Dose Adjustments

Temozolomide dose adjustments should be prescribed as clinically appropriate, as per the Investigator's discretion with consideration to the product label recommendations (which may be more conservative than the guidance below).

Initiation of TMZ should not begin until the patient's peripheral blood counts have recovered from chemoradiation such that absolute neutrophil count (ANC) is $\geq 1500/\mu L$ and platelet count is $\geq 100,000/\mu L$. Delays in the initiation of temozolomide will be recorded in the CRF.

During temozolomide cycles, up to a three-week dose delay in temozolomide administration may be considered until the patient's blood count returns to an acceptable level (ANC \geq 1500/ μ L and platelet count \geq 100,000/ μ L).

Deviations from the above-outlined treatment schedule are allowed and will not represent protocol violations, when appropriate as per standard of care. However, such deviations must be discussed with the Study Principal Investigator in advance to ensure appropriate visit scheduling.

Table 1 Temozolomide Dose Levels for Maintenance Treatment

Dose	Level Dose (mg/m2/day)	Remarks
-1	100	Reduction for prior toxicity
0	150	Dose during Cycle 1

1	200	Dose during Cycles ≥ 2 in absence of Grade 3 or higher toxicity
---	-----	--

Table 2 Temozolomide Dose Levels for Maintenance Treatment

Toxicity * Discontinue TMZ	Reduce TMZ by 1 Dose Level	Discontinue TMZ
Absolute Neutrophil Count	less than 1.0 x 10 ⁹ /L	See footnote†
Platelet Count	less than 50 x 10 ⁹ /L	See footnote†
CTC Non-Hematological Toxicity (except for alopecia, nausea, vomiting)	CTC Grade 3	CTC Grade 4†

^{*}TMZ dose levels are listed in **Table 1**

†TMZ is to be discontinued if dose reduction to less than 100 mg/m² is required or if the same Grade 3 non-hematological toxicity (except for alopecia, nausea, vomiting) recurs after dose reduction. TMZ=temozolomide; CTC=Common Toxicity Criteria.

If temozolomide is discontinued for any reason other than tumor progression, SVN53-67/M57-KLH vaccinations may continue at the Investigator's discretion

6.3 General Concomitant Medication and Supportive Care

The use of all standard supportive medication is permitted, although concurrent treatment with immunosuppressive or immunomodulatory agents is strongly discouraged. Concomitant systemic corticosteroids are to be avoided if at all possible. If used, doses of steroids should be the minimum necessary for appropriate clinical management. If any new or increased dose of steroids is necessary due to signs or symptoms, a rigorous evaluation for recurrent glioblastoma should be conducted and, in the absence of progressive disease, every effort should be taken to taper the patient off steroids as quickly as clinically feasible. If clinically necessary, topical or systemic non-steroidal anti-inflammatory or antihistamines may be used as alternatives.

When clinically appropriate, patients should strictly follow the study-prescribed treatment regimen. Therefore, patients should not receive additional investigational agents or anti-cancer therapies, unless progression of disease warrants discontinuation of study treatment and commencement of alternate therapies. Patients who begin new anti-cancer therapy, including investigational therapy, chemotherapy, cytokine therapy, immunotherapy (including other vaccines), or alternating electrical field therapy must discontinue SurVaxM, and will be followed for survival. Patients who undergo surgical resection or biopsy in the absence of progression may, upon consultation and agreement with Roswell Park Cancer Institute, be eligible to continue to receive study treatment with follow up to document persistent disease growth.

All concomitant medication will be documented in the CRF if taken within 30 days prior to Priming Phase through (whichever occurs first) either, a) 30 calendar days after the last

administration of study treatment or, b) initiation of alternate anticancer therapy. All concomitant medications required to treat study-drug related toxicity should be reported regardless of the timeframe relative to study drug dosing. All anti-cancer medications taken throughout the duration of study follow-up should also be recorded.

Participants may be pretreated for nausea and vomiting with appropriate anti-emetics.

6.3.1 Guidance for Management of Expected Toxicity

6.3.1.1 Local Injection Site Reaction

Based on the experience with SurVaxM and other peptide vaccines, local injection site reactions are likely to be the most common event associated with the administration of SurVaxM. However, not all patients may experience an injection site reaction with the first few administrations of vaccines, and not all patients who experience injection site reactions may experience a reaction with every injection of vaccine. Erythema and pruritus occurred most frequently, but localized swelling, pain, rash, induration, bruising and urticaria are also possible, and may be relatively common. Some injection site reactions may extend for multiple centimeters into the surrounding dermis and take up to several days to resolve.

The clinical experience to date suggests that nearly all injection site reactions are tolerable and resolve without the need for intervention. Topical corticosteroids are permitted to treat injection site reactions at the discretion of the investigator. Nevertheless, systemic corticosteroids should be reserved for severe injection site reactions only since they may also compromise the immune response to the vaccine and could negate its effect. Topical or systemic non-steroidal anti-inflammatory agents (e.g. ibuprofen, naproxen, aspirin) or antihistamines (e.g. Claritin®, Allegra®, Benadryl) may be used as alternatives; however, routine use to prevent injection site reactions should be avoided, and doses should be the minimum necessary for appropriate clinical management.

SurVaxM injection sites should be rotated in accordance with the applicable study protocol; injections should not be given to areas with evidence of persistent local reaction.

Injection site reactions are considered adverse events and should be reported as such, using an appropriate descriptive term. (For example, "injection site erythema" should be used rather than the less descriptive term "injection site reaction".) **Section 10.1.2.1** provides guidance for the severity ratings of possible injection site reactions.

6.3.1.2 Hypersensitivity Reactions

Hypersensitivity-like reactions could occur. Precautions should be taken to prepare for the possibility of anaphylactic/hypersensitivity reactions after SurVaxM/Montanide/sargramostim administration. Patients should be observed as per institutional standards, but for a minimum of 1 hour following each vaccination to evaluate and treat any potential immediate hypersensitivity reactions. The use of all routine supportive medication is permitted for hypersensitivity reactions, although routine use of prophylactic antihistamines, nonsteroidal anti-inflammatory agents and concomitant systemic corticosteroids are to be avoided if at all possible. If used, doses of steroids should be the minimum necessary for appropriate clinical management. If any new

administration of or increased dose of systemic steroids is necessary, every effort should be taken to taper, and preferably discontinue treatment with them, as quickly as clinically feasible.

For pain or fever, acetaminophen (325 mg tabs, 1 or 2 p.o. every 4 hours p.r.n.) will be utilized preferentially. Pretreatment of participants with acetaminophen may be instituted as warranted for a temperature of 38°C. Fevers lasting more than 8 hours after treatment will be evaluated in terms of potential infection. Aspirin, naproxen and ibuprofen are acceptable alternatives to acetaminophen for pain or fever, but are not preferred.

For mild to moderate local injection site pain that is unresponsive to acetaminophen, oral opiates will be used (oxycodone, 5–10 mg p.o. every 4 hours, p.r.n.). Pain that is of more than mild to moderate grade will be investigated for sources other than the therapy, and managed accordingly.

Anticonvulsant, antihypertensive and antidiabetic medications should be used as indicated. Antiemetics may be administered at the discretion of the treating physician.

For delayed hypersensitivity reactions, investigators should treat for symptomatic relief but avoid corticosteroid use whenever possible.

6.3.1.3 Non-Injection Site Rashes

Investigators should treat for symptomatic relief but should avoid systemic corticosteroid use if at all possible.

6.4 Duration of Treatment

Participants may remain on study and continue to receive treatment in the absence of: disease progression, unacceptable toxicity, intercurrent illness that prevents further administration of treatment, participant demonstrates an inability/refusal to comply with oral medication regime, or participant withdraws from study.

6.5 Duration of Follow-Up

All patients treated on study will be followed until death or loss of follow-up.

6.6 Treatment Discontinuation

Upon treatment discontinuation, all end of treatment evaluations and tests will be conducted. All participants who discontinue due to an AE must be followed until the event resolves or stabilizes. Appropriate medical care should be provided until signs and symptoms have abated, stabilized, or until abnormal laboratory findings have returned to acceptable or pre-study limits. The final status of the AE will be reported in the participant's medical records and the appropriate eCRF.

A patient should be withdrawn from study treatment if, in the opinion of the Investigator, it is medically necessary. In addition, patients will be withdrawn from treatment in the case of:

- 1. RANO criteria defined disease progression. In cases where RANO criteria cannot be applied, progression should be based on unequivocal evidence of progressive disease sufficient to require a change in therapy.
- 2. A need for surgery, radiation, or for other anticancer therapy not specified in the protocol.

- 3. Lost to follow-up or noncompliant.
- 4. Pregnancy. Pregnant patients should be followed for the duration of the pregnancy and the outcome of the pregnancy should be documented.
- 5 Death
- 6. Participant voluntary withdrawal
 - a. A participant may withdraw from the study at any time, for any reason. If a participant discontinues treatment, an attempt should be made to obtain information regarding the reason for withdrawal.
- 7. Investigator decision.

7 INVESTIGATIONAL PRODUCTS

7.1 **SVN53-67/M57-KLH (SurVaxM)**

The synthetic peptide in SurVaxM (SVN53-67/M57) spans amino acids 53 through 67 of the mature human (and mouse) survivin protein sequence and contains a substitution of methionine (M) for cysteine (C) at position 57 which leads to enhanced MHC class I binding. The peptide is conjugated to Keyhole Limpet Hemocyanin (KLH). SVN53-67/M57-KLH contains a peptide mimic that is immunogenic in humans and in C57BL/6 mice. The planned investigational study is based on extensive experimental observation concerning the ability of SurVaxM to elicit potent and specific immune responses that are capable of inhibiting the growth of cerebral gliomas in mice and killing human glioma cells ex vivo via cytotoxic T lymphocyte (CTL) activity.

7.1.1 Pharmacological Class

This peptide is to be used as a vaccine and is a biological drug by class.

7.1.2 Structural Formula

SVN53-67/M57-KLH is 15-amino acids in length with the amino acid sequence: DLAQMFFCFKELEGW. It is conjugated to Keyhole Limpet Hemocyanin (KLH), which serves as a carrier protein and immune adjuvant.

7.1.3 All Active Ingredients

SVN53-67/M57-KLH is conjugated to Keyhole Limpet Hemocyanin (KLH). SVN53-67/M57-KLH is administered emulsified in Montanide ISA 51 VG, (Cross-Referenced Drug Master File 10870, Seppic, Inc. France) and is co-administered with a separate local injection of sargramostim; Leukine®).

7.1.4 Drug Shipment

SVN53-67/M57-KLH will be shipped to all participating sites from The University of Iowa Pharmaceuticals as individual vials containing 1 mg sterile lyophilized powder in 2 mL clear

borosilicate glass crimped rubber stopper vials. Labeled boxes of peptide holding 80 vials each are supplied and shipped at -20°C in a Styrofoam insulated cardboard carton.

The date of receipt, condition of the shipment, and the amount of drug received will be documented. Drug shipment records will be retained by the investigational pharmacist or designee.

7.1.5 Preparation

Each vial of SVN53-67/M57-KLH peptide-conjugate, as delivered by The University of Iowa Pharmaceuticals, contains 1 milligram of lyophilized drug per vial. The peptide conjugate is reconstituted in the Investigational Drug Service Pharmacy with 1 mL sterile bacteriostatic saline injected into the primary 2 mL stock vial to yield a 1 mg/mL solution. The reconstituted solution will either be used for vaccine preparation or discarded.

7.1.6 Storage and Stability

Upon arrival, SVN53-67/M57-KLH is stored at -20°C in a locked, temperature alarmed and remotely monitored freezer under the control of the Investigational Drug Service Pharmacy. Stability testing will be performed on a regular schedule in accordance with applicable FDA regulations and the IND for SVN53-67/M57-KLH.

7.1.7 Handling and Disposal

The Investigator or designee will be responsible for prescribing all investigational drug provided by RPCI exercising accepted medical and pharmaceutical practices. Study drugs must be handled as cytotoxic agents and appropriate precautions taken per the institution's environmentally safe handling procedures. All investigational drugs will be dispensed in accordance with the Investigator's prescription or written order.

All products dispensed will be recorded on a product accountability record. Records of product lot numbers and dates received will be entered on a product accountability form. It is the Investigator's responsibility to ensure that an accurate record of investigational drug issued and returned is maintained.

Used vials (excess drug) will be destroyed according to standard practices after properly accounting for the dispensing. Partially used vials of study drug will not be re-used for other participants.

Under no circumstances will the Investigator supply investigational drug to a third party or allow the investigational drug to be used in a manner other than as directed by this protocol.

7.2 Vaccine Preparation: SVN53-67/M57-KLH, Montanide® ISA 51 and Sargramostim

For each vaccination, SVN53-67/M57-KLH will be mixed with Montanide® ISA-51 VG to create an emulsion using the standard operating procedures established in **Appendix D**. Sargramostim (Leukine) will be delivered locally as a separate injection.

Leukine (Sargramostim), NDC Product Code 50419, is an approved drug.

7.2.1 Interaction with Other Medicinal Products and Other Forms of Interaction

There have been no unexpected interactions observed between SurVaxM and other drugs as of the data cut-off date.

7.2.2 Overdose

No specific antidotes exist for the treatment of SurVaxM overdose.

7.2.3 Pregnancy, Lactation, and Pediatric Use

Fertility and teratology studies with SurVaxM have not been conducted. Safety for women of childbearing capacity cannot be implied from the existing data. Patients who are pregnant or are breast feeding are excluded from all SurVaxM clinical trials. Female patients must be surgically sterile or be postmenopausal, or must agree to use effective contraception during the period of treatment. All female patients with reproductive potential must have a negative pregnancy test prior to treatment with SurVaxM. Male patients must be surgically sterile or must agree to use effective contraception during the period of treatment. The safety of SurVaxM in pediatric patients has not been evaluated and, therefore, SurVaxM should not be administered to patients <18 years of age.

7.3 Adjuvant Temozolomide

Temozolomide will not be provided for this study and will be paid for by the patient's insurance carrier as part of the standard-of-care treatment of newly diagnosed glioblastoma.

8 STUDY PROCEDURES

Informed consent *MUST* be completed prior to receiving any study related procedures.

Unless otherwise defined in the written protocol text, all procedures/assessments will be conducted in accordance with RPCI Clinical Research Services Standard Operating Procedures.

8.1 Schedule of Investigations and Data Collection

The study is divided into phases with associated evaluations and procedures that must be performed at specific time points, as described in the following sections. The study Schedule of Procedures and Observations (**Table 3**) summarizes the frequency and timing of various activities, safety, and other measurements.

Every effort should be made to ensure that the protocol required tests and procedures are completed as described. However it is anticipated that from time to time there may be circumstances outside of the control of the investigator that may make it unfeasible to perform the test. In these cases the investigator will take all steps necessary to ensure the safety and well-being of the patient. When a protocol required test cannot be performed, the study investigator will document the reason for this and any corrective and preventive actions that have been taken to ensure that normal processes are adhered to as soon as possible. The study team will be informed of these incidents in a timely fashion.

8.1.1 Screening Period

Prior to the performance of any study-specific procedures, the patient will have the nature of the study explained to them, and will be asked to give written informed consent. Informed consent must be obtained prior to any study-specific procedures that do not form a part of the patient's normal care. However, assessments performed according to standard of care prior to receipt of informed consent may be utilized to fulfill the screening requirement, if completed within the required window for screening.

The assessments outlined for the Screening Visit in the study Schedule of Procedures and Observations (**Table 3**) will be completed for each patient prior to inclusion in the study, and results will be evaluated to verify entry criteria prior to study entry.

8.1.2 Treatment Phase

The patient should begin protocol treatment with Priming Vaccine Day 1 within 7-28 days after completion of standard chemoradiation. The study Principal Investigator is to be contacted for any extenuating circumstances that could prevent timely initiation of protocol treatment.

The on-study period will be divided into three components, to include the vaccine priming phase (four doses of SurVaxM), adjuvant temozolomide with SurVaxM (the adjuvant phase) and the SurVaxM maintenance period (the maintenance or boosting phase). Specific procedures to be performed throughout the treatment phases are illustrated in the Schedule of Procedures and Observations (**Table 3**).

8.1.3 Treatment Completion/Discontinuation

The End of Treatment Visit should be performed within 30 days (\pm 3 days) after last study drug dosing, or prior to initiation of alternate therapies (whichever occurs sooner). Follow-up and documentation of adverse events and concomitant medications should continue through day 30. Specific procedures to be performed at this visit are illustrated in the Schedule of Procedures and Observations (**Table 3**).

8.1.4 Post-Treatment Follow-up Phase

Patients who discontinue study treatment should be followed for survival with visits or phone contact every 12 weeks (\pm 4 weeks) until death or lost to follow-up.

.

 Table 3
 Schedule of Procedures and Observations

Protocol Activity	Screen	Vaccine Priming Phase ¹			Adjuvant Temozolomide ²	Vaccine Maintenance Phase ³	Disease Assessment	End of Treatment ⁴	Survival Follow-up ⁵	
		V1	V2	V3	V4	Day 1 of each 28 day cycle	Every 12-weeks (± 2 weeks)	Every 8 weeks (± 4 weeks)		Every 12 weeks (± 4 weeks)
Tumor tissue	X									
Medical history	X									
Physical examination	X	X	X	X	X	X	X	X		
Neurological examination/ MMSE ¹⁴										
Vital Signs(to include weight)	X	X	X	X	X	X	X	X		
Karnofsky Performance Status	X	X	X	X	X	X	X	X		
Hematology ⁶	X	X	X	X	X	X	X			
Chemistry ⁷	X	X	X	X	X	X	X			
Urinalysis	X	X	X	X	X					
Pregnancy Test (serum) ⁸	X	X	X	X	X	X				
HLA typing ¹³	X									
Humoral and Cellular Immune Reponses ⁹		X						X	X	
Brain MRI ¹⁰	X							X	X	
Study Vaccine		X	X	X	X		X			

Protocol Activity	Screen	V	accine Pri	ming Phas	e ¹	Adjuvant Temozolomide ²	Vaccine Maintenance Phase ³	Disease Assessment	End of Treatment ⁴	Survival Follow-up ⁵
		V1	V2	V3	V4	Day 1 of each 28 day cycle	Every 12-weeks (± 2 weeks)	Every 8 weeks (± 4 weeks)		Every 12 weeks (± 4 weeks)
Measurement of local reaction 15		X	X	X	X		X			
Adjuvant Temozolomide						X				
Concomitant Medications	X	X	X	X	X	X	X	X	X	X ¹¹
Adverse Events Assessment ¹²		X	X	X	X	X	X	X	X	
Contact Information for survival follow-up										X

Footnotes for Schedule of Procedures and Observations:

Note: Unless otherwise noted, study assessments should be completed prior to dosing at each treatment visit.

- 1. V1 within 7-28 days after completion of chemoradiation and then every two weeks (14 days \pm 3 days) for a total of 4 doses.
- 2. Adjuvant temozolomide therapy (TMZ) will begin ≥42 days after completion of concomitant temozolomide radiation therapy and given for 6 cycles or more (at the discretion of the investigator), or until intolerance or tumor progression. Temozolomide to be taken on Day 1 through Day 5 of each 28-day cycle ± one week window for tests and visit.
- 3. Maintenance Vaccine Phase: SurVaxM should be administered every 12 weeks (± 2 weeks) after the priming phase until intolerance or tumor progression (12-week cycle ± one week window for tests and visit).
- 4. The End of Treatment visit should be performed within 30 days (± 3 days) after last study drug dosing, or prior to initiation of alternate therapies (whichever occurs sooner). Follow-up and documentation of adverse events and concomitant medications should continue through day 30 (± 3 days), or until lost to death or follow-up.
- 5. Patients who discontinue study treatment should be followed on study for survival, with visits or phone contact every 12 weeks (±4 weeks) until death or lost to follow-up.

- 6. Hematology: CBC with differentials, platelets.
- 7. Chemistry: (CMP) defined as: chloride, CO₂, potassium, sodium, BUN, glucose, calcium, creatinine, total protein, albumin, total bilirubin, alkaline phosphatase, AST, ALT, A/G ratio, BUN/creatinine ratio, osmol (Calc), anion gap.
- 8. Pregnancy test is required for women of child bearing potential only. A serum pregnancy test must be performed during screening. If the serum pregnancy test is not performed within 7 days of dosing on Priming Phase V1-Day 1, a urine pregnancy test must be performed on Priming Phase V1-Day 1 with results reviewed prior to dosing. Testing may be repeated throughout the study as indicated.
- 9. Blood: six 10 mL green top tubes and one 3.5 mL gold top tube to be collected for in vitro immunological assays (see Section 8.2).
- 10. Brain MRIs must be obtained from the postoperative period (ideally with 72 hours) and post-chemoradiation period (within 1-14 days of completion of chemoradiation).
- 11. Subsequent to progression, medication review is limited to new anti-cancer regimens.
- 12. Documentation of adverse events occurring from the date the participant signs the study consent until 30 days after the last intervention or a new treatment is started, whichever occurs first. Any serious adverse event occurring any time after the reporting period must be promptly reported if a causal relationship to study treatment is suspected.
- 13. HLA –A low resolution panel
- 14. MMSE: Mini Mental State Exam will be done at the discretion of the PI. (41)
- 15. Patient to be instructed to check injection site for 24 to 48 hr post injection: staff to call within 3 to 5 days to document any reaction (see **Section 6.1.1**).

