6.2.1 SurVaxM Dose Omission or Discontinuation

Since all toxicities related to SurVaxM are expected to be immunologically mediated, no adjustment to the administered dose will be allowed.

If any unexpected significant toxicity (e.g., CTCAEv4 Grade 3) is observed, and there is a reasonable likelihood that the event may be associated with administration of SurVaxM and/or sargramostim, the next immunization for that patient should be withheld until the toxicity improves to mild severity or less. The immunization may be held for up to 2 weeks following the withheld dose. If significant toxicity is observed again or is not reversible, all further immunizations should be discontinued.

If vaccinations are discontinued for any reason, temozolomide administration may continue at the Investigator's discretion

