12.4 Sample Size Determination

The primary endpoint will be the 6 month PFS survival fraction. Let π represent the 6 month PFS survival fraction. A true rate of the 6 month PFS survival fraction greater than π_0 =0.55 is considered acceptable and evidence such that we will the treatment worthy of further study. The null and alternative hypotheses to be tested are H_0 : π = π_0 versus H_a : π > π_0 . We hypothesize that patients treated with SurVaxM and adjuvant temozolomide will have a 6 month PFS survival fraction of 0.70 or larger. The sample size calculation is based on testing the hypotheses concerning the proportion of the population with a response to the treatment: H_0 : π = π_0 versus H_a : π > π_0 . For our calculations π_0 =0.55, α =0.10, 1- β =0.80. Based on an exact one-sided test the sample size calculation yields n=50 patients.

Subjects will be accrued to the study on a first-come basis. The projected accrual is approximately 2 subjects per month, and therefore recruitment is expected to be complete at 25 months following the study starting point. Subjects will be followed to determine time to tumor progression (PFS) and until death to determine overall survival (OS).

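### Patients who stop treatment without progression go to survival-only follow-up, which conflicts with the promise to follow for PFS and leaves unknown 6-month status with no rule

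*Combined protocol and SAP*

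**What the plan says.** Section 8.1.4 sets the rule once treatment ends: "Patients who discontinue study treatment should be followed for survival with visits or phone contact every 12 weeks". Table 3 footnote 5 has the same rule: "Patients who discontinue study treatment should be followed on study for survival, with visits or phone contact every 12 weeks". Section 6.3 applies it to patients who begin another anti-cancer therapy; they "must discontinue SurVaxM, and will be followed for survival".

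In Table 3, Brain MRI is marked at Screening, at Disease Assessment (every 8 weeks, ± 4 weeks) and at End of Treatment. The Survival Follow-up column marks only concomitant medications and contact information. Section 8.1.3 places the End of Treatment visit within 30 days (± 3 days) "after last study drug dosing, or prior to initiation of alternate therapies (whichever occurs sooner").

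Stopping without progression is foreseen. The withdrawal reasons in Section 6.6 include noncompliance, pregnancy, the participant's choice, investigator decision and "A need for surgery, radiation, or for other anticancer therapy not specified in the protocol".

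On the endpoint side, Section 12.3 promises every patient at least 6 months of follow-up for the primary endpoint and defines PFS by progression or death. Section 12.4 states: "Subjects will be followed to determine time to tumor progression (PFS) and until death to determine overall survival (OS"). Section 12.7.1 estimates PFS6 as a binomial proportion and also treats patients alive and disease free at their last assessment as censored. Section 12.1.1 rules out imputation.

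**The concern.** The follow-up schedule and the endpoint sections ask for different things. A patient who completes priming, stops treatment without progression and has the End of Treatment MRI is then owed only a survival contact. If the patient is alive at month 6, the follow-up rule requires nothing that would show whether the tumor has progressed.

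The analysis section does not settle what happens next. A binomial proportion has no place for a censored patient: each one must be a success, a failure or out of the denominator. The plan does not say which, and replacement under Section 12.9 covers only missed priming doses and withdrawn consent. The primary test could therefore rest on a choice made after the data are seen. The PFS curve and median would also lose progression dates in patients who stop early.

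**Working it through.** **1. The plan's own figure.** Inputs from Sections 12.4 and 12.7.1: null rate 0.55, alternative 0.70, exact one-sided test at 0.10, power 0.80, n = 50. The critical value r is the smallest integer with P(X ≥ r | n, 0.55) ≤ 0.10. For n = 50, r = 33, with exact type I error 0.0765 and power P(X ≥ 33 | 50, 0.70) = 0.782. This is close to the stated 0.80, so the stated sample size is reproduced.

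**2. How long PFS6 is exposed.** An evaluable patient has had four priming doses (Section 12.1). Inputs from Sections 4.1 and 6.1: about 28 days of recovery, 42 days of chemoradiation, 7 to 28 days to the first dose, and 42 days from first to fourth dose. I assume that diagnosis is at surgery.

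- Earliest fourth dose: 28 + 42 + 7 + 42 = day 119.
- Latest fourth dose: 28 + 42 + 28 + 42 = day 140.
- Time left to month 6 (182.6 days): 182.6 − 119 = 63.6 days, or 182.6 − 140 = 42.6 days; about 6 to 9 weeks.
- Letting the ± 3-day window accumulate over three intervals (± 9 days) widens this to about 34 to 73 days.

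The End of Treatment MRI covers part of this. If the fourth vaccine dose is the last study drug and the visit is as late as allowed (33 days), it falls on day 152 or 173, leaving about 31 or 10 days to month 6.

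**3. What the handling of unknowns does.** Suppose k of 50 evaluable patients have unknown 6-month status, unrelated to outcome. The documents give no k, so 1 to 5 is shown. With m = 50 − k known:

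- Excluded: r is recomputed for m patients.
- Counted as failures: power = P(X ≥ 33 | m, 0.70).
- Counted as progression-free: type I error = P(X ≥ 33 − k | m, 0.55).

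| k | Excluded: rule | Type I error | Power | As failures: power | As progression-free: type I error |
|---|---|---|---|---|---|
| 1 | 32/49 | 0.095 | 0.810 | 0.717 | 0.095 |
| 2 | 32/48 | 0.068 | 0.750 | 0.642 | 0.117 |
| 3 | 31/47 | 0.085 | 0.780 | 0.559 | 0.142 |
| 4 | 31/46 | 0.060 | 0.713 | 0.470 | 0.172 |
| 5 | 30/45 | 0.076 | 0.746 | 0.380 | 0.206 |

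Power under exclusion does not fall smoothly, because the critical value moves in whole patients. Two unknowns counted as progression-free are enough to take the type I error above 0.10. Counting unknowns as failures is conservative but costs power quickly.

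**The case against.** A reader might infer that PFS simply cannot be observed once treatment stops. The documents do not support that. Contact may be a visit, an End of Treatment MRI is scheduled, and the 8-weekly Disease Assessment column has no stated end. Deaths are captured and are PFS events. Sections 12.3 and 12.4 state the intent to follow for progression. Stopping one agent also need not end treatment: "If vaccinations are discontinued for any reason, temozolomide administration may continue at the Investigator's discretion", and Section 6.2.2 allows the reverse.

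A reader might also infer that PFS6 is biased upward because early stopping tracks prognosis. Much of that route is closed. Section 9.2.1 already counts as progression both clear clinical deterioration and failure to return because of death or a deteriorating condition. Section 6.3 discourages other anti-cancer therapy unless progression warrants it. Section 12.9 replaces patients who withdraw consent. What remains could move the estimate either way, depending on how unknowns are counted.

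An example can be built in which the handling decides the trial: 30 successes among 45 known, with 5 unknown. Counted as failures this is 30/50 (p = 0.286); as successes, 35/50 (p = 0.022); excluded, 30/45 (p = 0.076). The arithmetic is right, but both counts are assumptions and 30/45 sits exactly on the critical value. It shows what is possible, not what to expect.

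What stands is that the survival-only rule makes no exception for patients without progression, and nothing clearly overrides it. The open-ended Disease Assessment column lets sites read the schedule either way.

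**Conclusion.** The conflict is real and worth correcting, at moderate importance. Sections 8.1.4 and 6.3 and Table 3 footnote 5 do not require the progression data that Sections 12.3 and 12.4 promise, and Section 12.7.1 has no rule for unknown 6-month status.

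For PFS6 the effect is probably confined to a few patients. This rests on the timeline above, with diagnosis taken at surgery, and on no documented discontinuation rate. The Kaplan-Meier curve and median PFS are more exposed, though Section 12.7.1 uses them descriptively. No direction of bias is established. The error rates in the table assume that unknown status is unrelated to outcome; if it is related, exclusion is no longer protected.

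It does not follow that starting a new anti-cancer therapy should count as a PFS6 failure. That is one convention among several. It departs from the progression-or-death definition in Section 12.3 and may not match how the 0.55 control rate was obtained, which the documents do not show. It could also cost power: three added failures whose status is unrelated to outcome take it from 0.78 to 0.56.

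**What to change.** Reconcile Sections 8.1.4, 6.3 and Table 3 with Sections 12.3 and 12.4. State in 8.1.4 and Table 3 that, for patients who stop without progression and have not withdrawn consent, progression status and date are recorded until progression or death, including after a new anti-cancer therapy starts. The sources would be routine-care MRI reports and clinical status, so no study procedure is added. Say whether the Disease Assessment column continues after treatment ends.

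In Section 12.7.1, keep the progression-or-death definition. State before analysis how an unknown 6-month status enters the binomial proportion. As a sensitivity analysis, report the result with all unknowns counted as failures and with all counted as successes.

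The cost is protocol and analysis wording, retrieval of routine scan reports for a few patients, and a little extra analysis. Routine scans will not follow the study timetable, so progression dates from them will be less exact than those from scheduled assessments.
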